7.5 Subject withdrawal

Under certain circumstances, an individual patient must be terminated from participation in this study. Specific events that will result in early termination include:

- Randomized after positive LFA results but prior to negative CLIA-approved ELISA test result,
- Need for respiratory support ends unexpectedly between time of randomization and first study product administration,
- Unexpected death between time of randomization and first study product administration,
- Subject has been inappropriately enrolled based on inclusion/exclusion criteria (e.g. when information through next of kin was inaccurate),
- Site investigator decides to terminate participation for reasons of patient's safety or to prevent compromising the scientific integrity of the study,
- It is determined that side effects are severe,
- New scientific developments indicate that the treatment is not in the patient's best interest,
- Patient or next of kin refuses further participation,
- Study is terminated.

Patients may be withdrawn at any time once the study team becomes aware that the patient meets one or more criteria for withdrawal. If the participant is withdrawn from the study before a dose of study product is given, no study procedures will be performed, no study data will be collected, and they will not be included in the primary analysis population. If a participant is withdrawn after receipt of study product, safety procedures (e.g. monitoring of creatinine and CBC with differential) will continue for another 48 hours, no further study biosamples will be obtained, study data in the medical record will continue to be collected per protocol and as allowed in the signed consent (e.g. respiratory-support-free days), and they will be included in the primary analysis population.

In the event that a participant does not start receiving first dose of study product within 120 hours after hospitalization, and this is discovered before 5 doses of study drug are administered, they must be withdrawn. In this circumstance, no further study procedures will be performed, no further study data will be collected, and they will not be included in the primary analysis population. If initiation of study drug past the 120-hour window is discovered after 5 or more doses of study drug have been given, the participant may remain in the study.

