3. GENERAL DATA ANALYSIS CONSIDERATION

3.1 Analysis Set(s)

The **Intent-to-Treat (ITT) Analysis Set** will include all enrolled and randomized participants. However, one exception applies: participants who are withdrawn from the study before receiving any dose of the study drug will not undergo study procedures and will be excluded from the ITT analysis. Participants who are withdrawn after receiving at least one dose will continue to receive safety assessments (e.g., creatinine and complete blood count with differential) for up to 48 hours. Although no study bio-samples will be collected after withdrawal, clinical data available in the medical record (e.g., respiratory-support-free days) will continue to be collected per protocol, and such participants will be included in the ITT analysis. **The ITT set will serve as the primary analysis population.**

Two modified Intent-to-Treat (mITT) Analysis Sets will also be defined:

The first mITT set will exclude participants who are withdrawn from the study for any reason after receiving at least one dose of study drug. Reasons for withdrawal may include, but are not limited to: participant withdrawal of consent, inability or unwillingness to comply with study procedures, refusal to continue participation by the participant or their legally authorized representative (LAR), or an initial positive CMV LFA test followed by a confirmatory negative CMV ELISA result.

The second mITT set will include only those participants who survive and are followed through day 28.

In addition, a **classical ITT set**, which includes all randomized participants regardless of treatment receipt or study completion, will be retained for completeness.

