6.2.4 Other pre-specified analyses

Primary analysis, cITT, mITT, and survivors

Ideally, any patient randomized would be included in the conventionally defined ITT analysis cohort. Nonetheless in an emergency care setting, such as this study, the following unusual but important scenario will need to be considered: a patient is eligible and randomized but by the time of drug delivery no longer meets eligibility criteria and thus, should have been excluded.

Accordingly, it is intended that patients randomized but not having drug/placebo delivered will not be included in the primary analysis cohort. The integrity of randomization shall remain preserved, as the decision to deliver drug/placebo is determined a priori and completely independent of treatment assignment (14). If a participant is withdrawn from the study before a dose of study drug is given, no study procedures will be performed and no study data will be collected, and these participants will be excluded from the primary analysis. However, if a participant is withdrawn after receipt of study drug, safety procedures (e.g. monitoring of

creatinine and CBC with differential) will continue for another 48 hours, no study biosamples will be obtained, and study data in the medical record will continue to be collected per protocol (e.g. respiratory-support-free days), and they will be included in the primary analysis. In addition to the primary analysis, we will also conduct a randomized or classical ITT analysis, which will consider all patients randomized. This will be used as a conservative alternative to our primary comparison. Additionally, we will also perform 2 modified intent-to-treat (mITT) analyses: 1) excluding patients who were withdrawn from the study for any reason (including initial positive CMV LFA test followed with confirmatory negative CMV ELISA test) after receiving at least one dose of study drug, and 2) only including patients who survived and were followed to day 28. We will also test for an interaction of treatment period (pre and post drug use) and the primary treatment differences at the study conclusion. Finally, we will perform subgroup analyses evaluating treatment effect stratified on mode of respiratory support.

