7.6 Subject replacement

A participant may be replaced in the study under certain circumstances of early withdrawal. The purpose of participant replacement is to compensate for potential data loss. The following circumstances may qualify a participant for replacement:

- Randomized after positive LFA results with subsequent negative CLIA-approved ELISA test result and before administration of study drug,
- Participant did not start receiving first dose of study product within 120 hours after randomization, and was withdrawn,
- Need for respiratory support ends unexpectedly between time of randomization and first study product administration,
- Unexpected death between time of randomization and first study product administration,
- Early termination between time of randomization and first study product administration (e.g., due to patient or next of kin refusing further participation, new scientific developments indicate that the treatment is not in the patient's best interest, or subject has been inappropriately enrolled based on inclusion/exclusion criteria),
- Participant who declines further participation and requests complete deletion of all data after regaining consciousness.

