9.5 Randomization procedure

Randomization will occur after assessment of positive CMV serostatus as detailed in **Section 9.3.1**, and negative pregnancy test. Randomization and first dose of study drug should occur as close to each other as possible. Randomization and first dose of drug **must** occur within 120 hours of hospital admission **and** on the same calendar day. Patients who are randomized but in whom the need for respiratory support ends, who die, are outside of the 120 hour window, or have consent withdrawn before receiving first dose of study drug should not receive their first dose of drug and are withdrawn from the study (see Section 7.5).

The randomization sequence will be uploaded by SCHARP into the MediData's Randomization and Trial Supply Management (RTSM) system and provided to each site through MediData. This

system automatically notifies the site pharmacist of the treatment assignment. The randomization will be block-randomized by site. At each institution, the pharmacist with primary responsibility for drug dispensing is charged with maintaining the security of the randomization list. Patients will be stratified at the time of randomization according to treatment center.

When the patient is randomized, the following information is required by NIH reporting guidelines: date of birth, race/ethnicity, and gender. For the purpose of this study, each patient will be assigned a study number, which will be used for all communications with outside institutions to assure confidentiality.

A CLIA-certified standard serologic assay will be used to confirm CMV positivity, but patients with a positive rapid test result may be randomized prior to the return of the CLIA test results (see **Section 9.3.1**).

Randomization will continue until the target accrual number for participants in the primary analysis are met. The primary analysis population will be all patients randomized who receive at least one dose of the assigned study product.

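### Protocol 7.5 drops some dosed late starters from the primary population and stops their data collection, contradicting protocol 6.2.1, 6.2.4 and 9.5 and SAP 3.1

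*Combined protocol and SAP*

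**What the plan says.** The primary population is defined by dosing. Protocol 9.5 states: "The primary analysis population will be all patients randomized who receive at least one dose of the assigned study product". Protocol 6.2.1 gives the same definition.

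Withdrawal after dosing does not remove a participant. Under the general rule in protocol 7.5, "study data in the medical record will continue to be collected per protocol and as allowed in the signed consent", and the participant still counts in the primary population. Protocol 6.2.4 agrees. SAP 3.1 names a single exception to its ITT set, withdrawal before any dose. Of those withdrawn after at least one dose it says "such participants will be included in the ITT analysis".

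The next paragraph of protocol 7.5 treats late starters differently. Where the first dose fell outside 120 hours from hospitalization and "this is discovered before 5 doses of study drug are administered, they must be withdrawn", the consequence is that "no further study data will be collected, and they will not be included in the primary analysis population". Where the late start is found at five or more doses, the participant is permitted to stay on study. The paragraph does not say which analysis set that participant belongs to.

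Protocol 7.6 lists a late start among the grounds for replacement, but with a different clock: "Participant did not start receiving first dose of study product within 120 hours after randomization, and was withdrawn". Exclusion criterion 3 and protocol 7.5, 9.5 and 9.7 all count from hospitalization or admission.

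**The concern.** Two analysts who follow these documents could build different primary populations. One would apply the dosing definition and keep a late starter who had three doses. The other would apply the late-start paragraph and leave that participant out. SAP section 12, on changes from the protocol, does not mention the matter, so the SAP cannot be read as having settled it.

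The exclusion happens after randomization and after dosing. Protocol 6.2.4 defends leaving out undosed participants on the ground that the decision to give drug is fixed beforehand and is independent of assignment. That argument does not reach an exclusion triggered by the moment at which an error is noticed.

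Stopping data collection also weakens the planned check. The classical ITT set takes in everyone randomized, but late starters withdrawn alive would have no RSFD value. SAP section 8 has no rule for them: its missing-data category covers withdrawn consent, refusal and study closure. Later vital status may be lost too, which matters in a trial whose enrollment was closed over safety and futility concerns (SAP section 4).

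**Working it through.** **1. One case under each passage.** Take a participant whose first dose was late and who has had three doses when this is found.

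| Source | Primary population | Outcome data |
|---|---|---|
| Protocol 6.2.1, 9.5 | In | Not addressed there |
| Protocol 6.2.4; 7.5 general rule | In | Continue from the medical record |
| SAP 3.1 | In | Continue from the medical record |
| Protocol 7.5 late-start paragraph | Out | Stop |
| SAP 3.1 classical ITT | In that set | Needed, but stopped by 7.5 |

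The late-start paragraph can be read as a specific exception to the general rule just above it. It cannot be squared with 6.2.1, 6.2.4, 9.5 or SAP 3.1, none of which mentions it.

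**2. What the five-dose threshold selects on.** Dosing is every 12 hours on days 1 to 5 (protocol 9.7). Dose 5 therefore falls 4 × 12 = 48 hours after dose 1, before any hold or renal adjustment. A late starter who dies or is discharged before then cannot reach the branch that allows staying on study. Surviving and remaining on drug for about two days is necessary for that branch, though not sufficient.

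**3. The plan's sample size.** Inputs from protocol 6.1.1: difference 2.74 days, SD 9.4, two-sided 5%, power 85%, 1:1 allocation.

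- Normal approximation: n = 2 × (1.960 + 1.036)² × (9.4/2.74)², which rounds up to 212 per arm.
- Two-sample t-test: 212.3, rounded up to 213 per arm, 426 in total. This reproduces the stated figure.

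The inflation to 500 allows for 1% loss to follow-up, 2% negative ELISA and an unstated factor for baseline PCR positivity. It makes no allowance for late starters.

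**4. Effect on power.** The share of late starters is not given, so 1% to 10% of 500 (5 to 50 participants) is assumed, removed without replacement and with the full 2.74-day effect. Power at 250 per arm is 90.3% with nobody removed, and 90.0%, 89.7%, 88.8% and 87.1% with 1%, 2%, 5% and 10% removed. Power is not the issue.

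**5. Deaths before dose 5.** Protocol 6.5.1.1 expects about 20% deaths. Treating this as 28-day mortality:

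- Constant hazard: 1 − 0.8^(2/28) = 1.6% die within two days.
- Threefold early hazard (assumed): 1 − 0.8^(6/28) = 4.7%.
- Expected deaths before dose 5 run from 5 × 0.016 = 0.08 to 50 × 0.047 = 2.35.

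At these rates at least 95% of late starters are alive at 48 hours, so most of those removed would be living participants.

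**6. Shift in an arm mean.** Removing k zeros from one arm of n = 250 with mean 16.33 (phase 2 control VFD mean in Table 6-1, standing in for RSFDs) shifts the mean by 16.33 × k/(250 − k):

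- k = 1: 0.07 days
- k = 2: 0.13 days
- k = 5: 16.33 × 5/245 = 0.33 days

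The expected counts in step 5, all placed in one arm, give about 0.005 to 0.16 days. The effect of removing living participants depends on RSFDs that would not be collected, so it cannot be computed.

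**The case against.** The strongest reply is that this is a small eligibility rule. Lateness is a breach of exclusion criterion 3 and is fixed at the first dose. Site staff other than pharmacists are blinded, so bias between arms would need early death, dose count or discovery to differ by arm within about two days. Patients expected to survive less than 72 hours are excluded. All of this stands, and it limits the size of the problem. It does not say which population definition governs.

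A reader might infer more than the documents support, in four ways.

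- **That the rule selectively removes early deaths.** It turns on discovery and dose count, not vital status. It removes living participants too, and early discharges, who would tend to have high RSFDs. The text does not say how someone already dead when the late start is found is classified.
- **That late starters found later are kept in the primary analysis by this rule.** The wording is permissive and names no analysis set. Their inclusion follows from the general definitions.
- **That deaths go unrecorded.** Only further data stop. Deaths on study are documented on the Study Termination CRF (protocol 11.2), so a death before withdrawal is known and scores zero. The gap concerns those withdrawn alive.
- **That 0.33 days is an expected bias.** It requires five removals, all deaths and all in one arm.

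The 120-hour clock in protocol 7.6 looks like a drafting slip. Protocol 9.5 and 9.7 require randomization and first dose on the same day, so a window of 120 hours from randomization could hardly operate. It bears on replacement only.

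**Conclusion.** The contradiction is established by comparing the texts and needs no assumption. Protocol 7.5 removes dosed late starters found before five doses from the primary population and ends their data collection. Protocol 6.2.1, 6.2.4 and 9.5 and SAP 3.1 keep them. The classical ITT set is left without RSFDs for those withdrawn alive.

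This is a post-randomization exclusion that depends on when the error is noticed and on doses given, and the retention branch requires reaching dose 5. Selection on early survival is therefore possible, but its size cannot be computed because the documents do not give the number of late starters, their split by arm or their outcomes. It is probably small: at most about 0.16 days on the assumed rates, and about 0.33 days in the extreme case of five deaths removed from one arm, against a design difference of 2.74. These figures rest on 250 per arm as planned, a phase 2 VFD mean and an assumed 1% to 10% late-start share. The documents do not show that either arm is favoured. The point should be corrected, but it does not by itself put the primary result in doubt.

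**What to change.** - **Population.** Make protocol 7.5 and SAP 3.1 say the same thing: every randomized participant with at least one dose stays in the primary population, whenever a late start is found.
- **Data.** For those already withdrawn, obtain RSFDs and vital status from records as consent allows. Protocol 5.4 already plans a medical-record review, and protocol 9.11 allows death registry records when a participant cannot be reached at day 180. State in SAP section 8 how a late starter with no obtainable outcome is handled.
- **Sensitivity analysis.** Put any exclusion of late starters there. The first mITT set already omits those withdrawn after dosing; an analysis omitting all late starters, whenever found, would be a separate set.
- **Reporting.** Give the number of late starters by arm, split by discovery before or after five doses, in the CONSORT diagram and with the deviation listing in SAP 6.3.
- **Reconciliation by the sponsor.** The 120-hour reference point differs between protocol 7.6 and the other sections. The two paragraphs of 7.5 also differ on whether safety procedures continue after a dosed withdrawal. Both must be reconciled. Whether study drug continues after a late start is left to the sponsor.

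The cost is wording in the protocol and SAP plus retrospective chart review. The number of charts is not stated; 1% of 500 would be five. Enrollment has closed, so recovery of outcomes may be incomplete where consent does not permit it.

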7.6 Subject replacement

A participant may be replaced in the study under certain circumstances of early withdrawal. The purpose of participant replacement is to compensate for potential data loss. The following circumstances may qualify a participant for replacement:

- Randomized after positive LFA results with subsequent negative CLIA-approved ELISA test result and before administration of study drug,
- Participant did not start receiving first dose of study product within 120 hours after randomization, and was withdrawn,
- Need for respiratory support ends unexpectedly between time of randomization and first study product administration,
- Unexpected death between time of randomization and first study product administration,
- Early termination between time of randomization and first study product administration (e.g., due to patient or next of kin refusing further participation, new scientific developments indicate that the treatment is not in the patient's best interest, or subject has been inappropriately enrolled based on inclusion/exclusion criteria),
- Participant who declines further participation and requests complete deletion of all data after regaining consciousness.

8 STUDY DRUG ACQUISITION, PREPARATION, & ADMINISTRATION

8.1 Study drug & placebo formulation

Intravenous ganciclovir and matching placebo.

8.2 Acquisition of study drugs & placebos

Study drug will be purchased by UW Pharmacy and supplied to study sites. In the event that UW Pharmacy is unable to source sufficient supply or if the drug cannot be directly supplied (e.g. to international sites), study drug from a commercial supplier may be used or purchased directly by study sites (costs to be passed through to the CCC). This provides necessary flexibility to prevent disruption of per-protocol administration of study drug due to global supply chain challenges or drug shortages. The drug supply must be FDA approved commercial ganciclovir sourced from a licensed distributor/manufacturer. The site will be responsible to appropriately document all doses prepared from local drug supply.

8.3 Storage of study drugs & placebos

Study drug will be stored as per manufacturer's recommendations.

8.4 Administration of study drugs & placebos

Ganciclovir (or IV placebo) will be administered via central or peripheral venous access.

Ganciclovir doses must be adjusted according to renal function as per package insert. A subject who is on hemodialysis should continue IV dosing according to the package insert.

8.5 Pharmacy Records

The site pharmacist is required to maintain complete records of all study drugs received from the sponsor or purchased by the site and subsequently dispensed. When using site supplied drug, sites are to maintain a record of manufacturer/lot number used for dose preparations.

9 CLINICAL PROCEDURES

9.1 Patient identification & recruitment

Patients with sepsis-associated acute respiratory failure will be identified via prospective screening of all ICU patients. This process is done by trained and experienced research coordinators who review charts using a standardized screening tool. Additionally, patients may be identified by the attending physician based on eligibility criteria.

9.2 Informed Consent

Informed consent is the essential processes of ensuring that study subjects or legal guardians fully understand what will and may happen to them while participating in a research study. Before any protocol-specific questions are asked or procedures to determine protocol eligibility performed, a screening consent form or protocol-specific consent form (described below) must be obtained. Patients or family members must be provided with a copy of all consent forms that they sign.

Since all potential patients will be intubated and sedated or requiring high levels of respiratory support, initial consent for patients who cannot make decisions for themselves will be from the patients' LAR. Subsequent consent from the patient will be obtained whenever possible. Interested surrogates will be given information about the study, explaining potential risks. They will then undergo informed consent. Consent forms will be approved by the Human Subjects Committee.

Participation in this study is voluntary. The nature of the study will be fully explained to each patient during the informed consent process. If the patient is deemed unable to provide written informed consent, informed consent for the patient's participation must be obtained from a LAR using practices and procedures that are acceptable as defined by local law and the Institutional Review Board. In this situation (the use of surrogate consent), subsequent in-person consent will be obtained from the patient when possible before hospital discharge. In circumstances where the patient has regained the capacity to consent but is discharged before study personnel have an opportunity to schedule an in-person meeting, then a remote consent method of phone/video conference will be used instead. The patient (or authorized representative, when applicable) will have the opportunity to ask questions. The patient (or authorized representative, when applicable) and the individual who performs the consent discussion will sign an informed consent document. The investigator will retain the informed consent document according to Good Clinical Practice. HIPAA authorization will also take place during the informed consent process.

The determination of appropriate "next-of-kin" will be made in accordance with the standard practices used in provision of medical care. Detailed documentation of all attempts to obtain consent from the patient and/or the patient's next-or-kin will be kept.

